1.0 TRIAL SUMMARY

Title	Phase I/II study of pembrolizumab in patients failing to respond to or relapsing after anti-CD19 chimeric antigen receptor modified T cell therapy for relapsed or refractory CD19+ lymphomas
Abbreviated Title	Pembrolizumab after CTL019/CTL119 for relapsed/refractory CD19+ lymphomas
Trial Phase	Phase I / II
Clinical Indication	Relapsed / refractory CD19+ B cell lymphomas after CTL019/CTL119
Trial Type	Investigator-initiated
Type of control	None. Enrollment will be offered to subjects with an unmet medical need, which is no available effective, standard therapy for relapsed / refractory CD19+ lymphomas
Route of administration	Intravenous
Trial drug, dose, route, regimen	Pembrolizumab (Keytruda [®]) 200mg fixed dose IV every 3 weeks
Trial Blinding	None
Treatment Groups	Single group
Number of trial subjects	12 evaluable subjects
Estimated enrollment period	12 months (approximately January 2016-January 2017)
Estimated duration of trial	36 months (approximately January 2016-January 2019)
Duration of Participation	24 months (12 months treatment + 12 months follow-up)
Objectives	
Primary Endpoints:
 
 1. Determine safety of pembrolizumab after CTL019/CTL119. This endpoint will be met if $\leq 30\%$ of patients develop toxicity resulting discontinuation of pembrolizumab. 2. Determine efficacy of pembrolizumab after CTL019/CTL119. This endpoint will be met if the ORR at 3 months is $\geq 35\%$.
Statistical methodology	
Primary Endpoints:
 
 1. Safety endpoint will be assessed using a Bayesian monitoring rule to ensure probability of a patient developing toxicity resulting in discontinuation of pembrolizumab $\leq 30\%$ 
Secondary Endpoints:
 
 1. ORR will be assessed using a one-sided binomial test 2. PFS, EFS, RD, and OS will be assessed using Kaplan Maier survival analysis. PFS after pembrolizumab will be compared to PFS after CTL019/CTL119 using a log rank test.

This document is confidential and the property of the University of Pennsylvania. No part of it may be transmitted, reproduced, published, or used by other persons without prior written authorization from the regulatory sponsor.

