2.0 TRIAL DESIGN

2.1 Trial Design

This is a single center, open label trial of pembrolizumab in patients failing to respond to or relapsing after anti-CD19 chimeric antigen receptor modified T cell therapy (CTL019/CTL119) for relapsed or refractory CD19+ lymphomas.

Eligible patients will have CD19+ diffuse large B-cell, follicular, or mantle cell lymphomas with no available curative treatment options, a limited prognosis of several months to <2 years anticipated survival with currently available therapies, and progressive or relapsed disease after a single intravenous dose of $5 \times 10^8 \pm 20\%$ CTL019/CTL119 administered on our currently enrolling clinical trial (NCT02030834). We anticipate enrollment of 12 total patients onto the present trial for patients not responding to, or relapsing after, CTL019/CTL119.

[figure not shown]
The safety and efficacy of pembrolizumab in this group of patients will be determined using a fixed dose of 200mg IV. This dose was previously well-tolerated and effective for treatment of patients with metastatic melanoma and NSCLC. The primary safety endpoint will be determined by assessing the rate of pembrolizumab discontinuation as well as the rate of occurrence of treatment-related adverse events (AEs), defined as NCI CTCAE version 5 grade ≥ 3 AEs are possibly, probably, or definitely related to study treatment or grade 4 cytokine release syndrome. Secondary efficacy endpoints will be assessed, including overall response rate (ORR) and progression-free survival (PFS).

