3.2 Secondary Objectives & Hypotheses

(1) Objective: To describe the overall response rate (ORR) at 3 months to pembrolizumab in patients failing to respond to or relapsing after CTL019/CTL119 for relapsed or refractory CD19+ lymphomas. To describe the clinical efficacy of pembrolizumab, including progression-free survival, disease-free survival, event-free survival, response duration, and overall survival (Cheson, 2007) in patients failing to respond to or

This document is confidential and the property of the University of Pennsylvania. No part of it may be transmitted, reproduced, published, or used by other persons without prior written authorization from the regulatory sponsor.

relapsing after CTL019/CTL119. Efficacy comparisons will be made for ORR between CTL019/CTL119 and pembrolizumab.

Hypothesis: Pembrolizumab will enhance the efficacy of CTL019/CTL119 in patients failing to respond to or relapsing after CTL019/CTL119 for relapsed or refractory CD19+ lymphomas (John, 2013).

- (2) **Objective:** To describe the immunophenotypic and cytokine profiles of chimeric antigen receptor modified T cells in these patients before and after therapy with pembrolizumab

Hypothesis: Immunophenotypic profiles of tumor cells and chimeric antigen receptor modified T cells obtained pre and post pembrolizumab therapy will identify patients for whom pembrolizumab will enhance efficacy.

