8.1.2 Secondary Objectives & Hypotheses

Any patient who receives at least one dose of pembrolizumab will be included in efficacy analyses.

(1) Objective: To describe the overall response rate (ORR) to pembrolizumab in patients failing to respond to or relapsing after anti-CD19 chimeric antigen receptor modified T cell therapy for relapsed or refractory CD19+ lymphomas.

Methodology: For efficacy, a sample size of 12 patients achieves an 80% power to detect a difference (P1 0.35 – P0 0.05) of 0.30 using a one-sided binomial test for ORR. The target of significance level is 0.05. This response rate prediction of 35% is based on the reported 28% response rate reported for nivolumab, another anti-PD1 blocking antibody, in patients with B cell lymphoma. This also assumes that a 5% response rate would be seen if pembrolizumab does not have efficacy in this population. If the response rate is 3 or more, the hypothesis that the ORR is ≤ 0.05 is rejected. If the number of responses is 2 or less, the hypothesis that ORR is ≥ 0.35 .

Hypothesis: The response rate after pembrolizumab will be 3 or more, allowing us to reject the null hypothesis that pembrolizumab after CTL019/CTL119 has an ORR ≤ 0.05

(2) Objective: To describe the clinical efficacy of pembrolizumab, including progression-free survival, disease-free survival, event-free survival, response duration, and overall survival (Cheson, 2007) in patients failing to respond to or relapsing after anti-CD19 chimeric antigen receptor modified T cell therapy for relapsed or refractory CD19+ lymphomas. Efficacy comparisons will be made with both most recent prior therapy as well as with CTL019/CTL119.

Methodology: Kaplan Meier survival analysis will be used to estimate progression-free survival, event-free survival, response duration, and overall survival. For patients with initial responses to both CTL 019 and pembrolizumab, progression-free survival, event-free survival, and response duration, patients' response to CTL 019 therapy will be compared to their response to pembrolizumab using the log-rank test, with $p \leq 0.05$ considered statistically significant.

Hypothesis: Pembrolizumab will enhance the efficacy of CTL019/CTL119 in patients failing to respond to or relapsing after chimeric antigen receptor modified T cell therapy for relapsed or refractory CD19+ lymphomas.

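### The log-rank comparison of pembrolizumab with CTL019 is made in patients selected for CTL019 failure, so its p-value cannot support an enhancement claim in either direction; it should be descriptive

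*Combined protocol and SAP*

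**What the plan says.** **The test.** Section 8.1.2, objective (2), covers PFS, event-free survival and response duration. "For patients with initial responses to both CTL 019 and pembrolizumab", patients' "response to CTL 019 therapy will be compared to their response to pembrolizumab using the log-rank test", and p ≤ 0.05 counts as significant. Sidedness is not stated, and no paired, patient-stratified or robust version is named.

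**The Summary.** Section 1 says "PFS after pembrolizumab will be compared to PFS after CTL019/CTL119 using a log rank test". It sets no responder restriction and no significance level.

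**Related comparisons.** Section 3.2 adds "Efficacy comparisons will be made for ORR between CTL019/CTL119 and pembrolizumab". Section 8.1.2 adds "Efficacy comparisons will be made with both most recent prior therapy as well as with CTL019/CTL119".

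**The hypothesis.** Section 8.1.2 places these comparisons under "Pembrolizumab will enhance the efficacy of CTL019/CTL119 in patients failing to respond to or relapsing after chimeric antigen receptor modified T cell therapy". Section 3.2 has nearly the same sentence.

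**Who can enter.** Section 2.1 requires "progressive or relapsed disease after a single intravenous dose" of CTL019/CTL119. Section 5.1.1 requires relapsed or refractory disease after it. Exclusion 1 in Section 5.1.3 admits CTL019/CTL119 recipients once progression or non-response is documented. Exclusion 2 bars lymphoma therapy given after CTL019/CTL119.

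**The concern.** The two sets of times are not selected alike. A patient reaches this trial only after CTL019 has failed, so the CTL019 time is a completed failure time by design, and patients in lasting remission after CTL019 never contribute. Nothing comparable cuts short the pembrolizumab times, which may run on or be censored. A difference between the curves could arise with no difference in effect.

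In the other direction, pembrolizumab is given later in the disease course. If prognosis is worse by then, that pulls the comparison toward CTL019. With no concurrent control, the two influences cannot be separated from a drug effect.

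At stake is the reading of a p-value placed under a hypothesis of enhanced efficacy. The primary safety endpoint and the ORR test against 5% are not affected.

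**Working it through.** **1. The plan's own figure.** No sample size, event count or power is given for the log-rank comparison. The only efficacy design figure is for ORR in Section 8.1.2: 12 patients, 5% against 35%, one-sided 0.05, 80% power, success at 3 or more responses. By exact binomial, P(X ≥ 3 | 12, 0.05) = 0.0196 and P(X ≥ 3 | 12, 0.35) = 0.849. With 11 patients the power is 79.99%, so 12 is the smallest number reaching 80%. That test is sound and can carry the efficacy conclusion.

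**2. Selection in the documents' counts (Section 4.2.1).**
- CTL019 responders: 7 of 7 follicular and 6 of 12 DLBCL, so 13 of 19 = 68%.
- Responders who had failed: 1 follicular, and at most 1 DLBCL (5 of 6 were in ongoing complete response).
- Responders who could not yet enter: at least 13 − 2 = 11 of 13.
- CTL019 responders among those who had failed: 1/(6 + 1) = 14% to 2/(6 + 2) = 25%.

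This is an early snapshot without mantle cell data, and later relapses would raise that share. The argument itself rests on the eligibility text.

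**3. Size of the set in Section 8.1.2.** Let q be the share of entrants who first responded to CTL019. Assume 35% respond to pembrolizumab, independently of CTL019 response. The number responding to both is Binomial(12, 0.35q), with mean 4.2q.

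| q | Expected patients | P(2 or fewer) |
|---|---|---|
| 25% | 1.05 | 92% |
| 50% | 2.1 | 65% |
| 68% | 2.9 | 42% |
| 100% | 4.2 | 15% |

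**4. Smallest attainable p.** Take n pairs with distinct event times and every CTL019 failure before any pembrolizumab event. Summing over i = 0 to n − 1, E = Σ(n − i)/(2n − i), V = Σ n(n − i)/(2n − i)², and z = (n − E)/√V.
- n = 1: z = 0.5/√0.25 = 1.00, two-sided p = 0.32.
- n = 2: E = 1/2 + 1/3, V = 1/4 + 2/9, z = 1.70, p = 0.090 (one-sided 0.045).
- n = 3: E = 1/2 + 2/5 + 1/4 = 1.15, V = 0.25 + 0.24 + 0.1875 = 0.6775, z = 1.85/0.823 = 2.25, p = 0.025.

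These are asymptotic values. The exact two-sided permutation minimum, 2/C(2n, n), is 2/20 = 0.10 for 3 pairs and 2/70 = 0.029 for 4. Two-sided significance therefore needs at least 3 pairs asymptotically and 4 exactly.

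**5. Illustration for the Section 1 reading only, taking both sets of times from the same 12 patients.** Assumptions: exponential times with a 6-month median after CTL019; CTL019 times kept only if failure falls within a window; pembrolizumab times censored at 24 months, the initial imaging period in Section 6.3; an ordinary log-rank test read at |z| ≥ 1.96. Correlated times share a log-normal patient frailty with SD 1. The later-line hazard ratio is the true hazard after pembrolizumab relative to that after CTL019. Values are rounded from simulation.

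| Window | Later-line hazard ratio | Result, independent / correlated |
|---|---|---|
| none | 1 | about 3% / 1% favour pembrolizumab |
| 12 months | 1 | about 31% / 18% favour pembrolizumab |
| 24 months | 1 | about 4% to 7% favour pembrolizumab |
| 12 months | 1.5 | about 6% / 3% favour pembrolizumab |
| 24 months | 2 | about 27% / 10% favour CTL019 |

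The nominal rate is 2.5% in each direction. Under equal hazards, the excess favouring pembrolizumab comes from selection. Without selection, positive correlation alone takes the rate below nominal, so ignoring the pairing is conservative. With equal hazards and a different correlation model (a Gaussian copula, correlation 0 or 0.5), medians of 6 to 24 months and windows of 12 or 24 months gave 1.6% to 98.7% favouring pembrolizumab. The size therefore depends mainly on assumptions the documents do not settle.

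**The case against.** The best reply is that this is a secondary analysis under an objective that sets out to describe, with no power claim, stopping rule or decision attached. That limits the consequence. It does not remove the problem, because the method sets a significance threshold under an enhancement hypothesis. Section 8.1.3 labels its own within-patient comparisons as descriptive; Section 8.1.2 does not do so for this one.

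Four further objections stand and limit the point:
- A reader might infer that the test is definitely unpaired. The plan names only the log-rank test. It neither specifies nor rules out a patient-stratified form, and pairing is a minor matter here.
- A reader might infer that the comparison is biased toward pembrolizumab overall. Only the selection component has that direction. As the last row of the table shows, a worse later-line prognosis can reverse the net result.
- A reader might apply the 31% to the Section 8.1.2 analysis. The illustration does not condition on response, so it does not describe responders to both. For that set only its likely size is shown.
- A reader might infer that the Section 3.2 ORR comparison has the same selection. Section 3.2 does not say that its CTL019 side is the same patients. Set against the 68% in Section 4.2.1, a 35% ORR would look worse, not better.

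Deletion is also not the only remedy: an explicit exploratory label would deal with part of the inference. It would leave a p-value whose direction of bias is unknown.

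**Conclusion.** The point holds for the inference, not for a fixed direction of bias. A log-rank p-value from patients admitted because CTL019 failed, with no concurrent control, cannot support enhancement of CTL019 efficacy, whichever therapy it favours.

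On the Section 8.1.2 reading, the set is expected to hold about 1 to 4 of 12 patients. This assumes 35% pembrolizumab response, independence, and 25% to 100% of entrants having first responded to CTL019. Often it would be too small to reach 0.05 at all. On the Section 1 reading, the false-positive rate ranges from near nominal to several times nominal depending on the assumed median and window, and the net direction also depends on later-line prognosis.

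The differing analysis sets are a separate inconsistency to reconcile. So is the comparison with most recent prior therapy. Because exclusion 2 bars intervening treatment, that therapy is CTL019/CTL119 itself unless the one before it is meant.

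The plan should be changed, but no primary conclusion depends on it.

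**What to change.** Remove the log-rank test from Sections 1 and 8.1.2, together with the p ≤ 0.05 criterion. Replacement text could read:

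*For every patient who received pembrolizumab, PFS and EFS after CTL019/CTL119 and after pembrolizumab will be listed and plotted side by side, with response duration where a response occurred and CTL019 responders marked. Kaplan-Meier estimates will be given for pembrolizumab only. Because entry requires failure of CTL019/CTL119, the comparison is descriptive and no test of the difference will be made.*

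Also:
- Use this one analysis set in both sections.
- Label the Section 3.2 ORR comparison as descriptive and say which CTL019 patients it uses. There is no concurrent control and, if the same patients are meant, the same selection applies.
- Label the comparison with most recent prior therapy as descriptive. Define it as the last therapy before CTL019/CTL119, or delete it as a duplicate.
- Do not use these comparisons to support the enhancement hypothesis in Sections 3.2 and 8.1.2. Rest the efficacy conclusion on the ORR test against 5%.

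The cost is wording in Sections 1, 3.2 and 8.1.2 and the loss of a nominal p-value. The data and visits are unchanged.

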8.1.3 Exploratory Objectives

(1) Objective: To describe the immunophenotypic and cytokine profiles of chimeric antigen receptor modified T cells in these patients before and after therapy with pembrolizumab

Hypothesis: Immunophenotypic profiles of tumor cells and chimeric antigen receptor modified T cells obtained pre and post pembrolizumab therapy will identify patients for whom pembrolizumab will enhance efficacy.

(2) Objective: For immunologic correlative studies, within subject comparisons of baseline to post pembrolizumab measures will be conducted. These analyses will be descriptive and considered exploratory; thus, power will not be considered for these paired comparisons.

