3.3 Exploratory Objective

- (1) **Objective:** To describe the baseline immunophenotypic profiles of tumor cells in these patients (see below chart).

Panels for polychromatic flow cytometry

Tumor: CD19 quant.	Tumor: inhibitory ligands	Tumor: costim & immune escape	T-cells: function (post Ag stimulation)	T-cells: inhibitory receptors, differentiation	T-cells: inhibitory receptors 2	T-cells: inhibitory receptors 3	T-cells: activation, HSC	T-cells: T-helper subsets, T-reg
8 colours	10 colours	13 colours	12 colours	13 colours	9 colours	7 colours	15 colours	12 colours
CD19	CD19	CD19	CAR19	CAR19	CAR19	CAR19	CAR19	CAR19
			CD3	CD3	CD3	CD3	CD3	CD3
CD20	CD20	CD20	CD4	CD4	CD4	CD4	CD4	CD4
CD5 or CD10	CD5 or CD10	CD5 or CD10	CD8	CD8	CD8	CD8	CD8	CD8
Ig λ		CD34		CCR7			CD34	
Ig κ				CD45RO			CD45RO	CD25
CD45	CD45	CD45		CD28			CD27	CD127
	CD200/Ox2	CD80/B7.1	CD107a	CD57	CD160	CD200R	CD134/Ox40	CCR4
CD3	CD270/HVEM	CD86/B7.2	GM-CSF	CD95	CD258/LIGHT	CD244/2B4	CD137/4-1BB	CCR6
	CD273/PD-L2	CD54/ICAM-1	IFN-γ	CTLA-4	CD272/BTLA		CD154/CD40L	CCR10
	CD274/PD-L1	CD162/PSGL-1	IL-2	PD-1	LAG-3		CD278/ICOS	CXCR3
		HLA-A,B,C	MIP-1α	TIM-3			HLA-DR	CXCR5
	Galectin-9	HLA-DR	MIP-1β				Ki67	
		HLA-G	TNF				Perforin	
dead/CD16	dead/CD16	dead/CD16	dead/CD14	dead/CD14	dead/CD14	dead/CD14	dead/CD14	dead/CD14

This document is confidential and the property of the University of Pennsylvania. No part of it may be transmitted, reproduced, published, or used by other persons without prior written authorization from the regulatory sponsor.

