7.1.1.13 Tumor Tissue Collection and Correlative Studies Blood Sampling

Blood may be optionally collected for correlative studies up to 3 days before pembrolizumab administration during cycles 1, 2, 3, and 4. Further optional blood draws may occur at time of routine laboratory study blood draws scheduled near time of imaging. These labs may be collected within 7 days before that week's dose of pembrolizumab.

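### The correlative analysis given in 8.1.3 is a before/after comparison that never uses response, so it cannot address the hypothesis that profiles identify who benefits

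*Combined protocol and SAP*

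**What the plan says.** Section 3.2 lists, as secondary objective (2), a description of the CAR T-cell profiles before and after pembrolizumab. Its hypothesis reads: "Immunophenotypic profiles of tumor cells and chimeric antigen receptor modified T cells obtained pre and post pembrolizumab therapy will identify patients", and the sentence goes on to specify patients in whom pembrolizumab will enhance efficacy. No method is given there.

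Section 8.1.3 repeats the objective ("To describe the immunophenotypic and cytokine profiles of chimeric antigen receptor modified T cells in these patients before and after therapy with pembrolizumab") and the hypothesis (profiles "pre and post pembrolizumab therapy will identify patients for whom pembrolizumab will enhance efficacy"), now under the exploratory heading. It then gives the analysis: "within subject comparisons of baseline to post pembrolizumab measures will be conducted". It adds: "These analyses will be descriptive and considered exploratory; thus, power will not be considered for these paired comparisons".

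Section 3.3 has one further aim, also descriptive: "To describe the baseline immunophenotypic profiles of tumor cells in these patients". It tabulates nine flow cytometry panels. Sections 6.5 and 7.1.1.13 cover sampling, which is optional: "Blood may be optionally collected for correlative studies up to 3 days before pembrolizumab administration during cycles 1, 2, 3, and 4". The efficacy methods in 8.1.2 (one-sided binomial test, Kaplan-Meier, log-rank) involve no marker.

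**The concern.** The hypothesis is about differences between patients: which of them gain from pembrolizumab. The stated analysis is about change within patients, averaged over all of them, and response does not enter it. Followed as written, it delivers a result that sits beside the hypothesis without bearing on it.

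Two things could follow. A before/after shift could be read as support for a selection marker when it is not. Or a responder comparison could be devised after the data are seen, with many markers to choose from and no record of which ones mattered beforehand. The ranking conflict adds to this: if the secondary rank in 3.2 stands, a secondary hypothesis has no analysis that addresses it.

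**Working it through.** **The plan's own figure.** 8.1.3 states no sample size or power for the correlative work, so there is nothing to reproduce there. The only sample-size figure is for ORR in 8.1.2: 12 patients, 80% power, 5% versus 35%, one-sided 0.05, reject at 3 or more responses. Exact binomial check:

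- Alpha = 1 − [0.95^12 + 12(0.05)(0.95^11) + 66(0.05²)(0.95^10)] = 0.0196.
- Power = 1 − [0.65^12 + 12(0.35)(0.65^11) + 66(0.35²)(0.65^10)] = 0.849.
- With 11 patients, power is 79.99%, so 12 is the smallest number that meets 80%. The figure is reproduced.

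**Responders expected among 12.** 12 × 0.35 = 4.2 at the target ORR; 12 × 0.28 = 3.4 at the nivolumab rate cited in 8.1.2; 12 × 0.05 = 0.6 at the null rate.

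**What each analysis estimates.** Let μ1 and μ0 be the mean marker change in responders and non-responders, and π the response proportion.

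- The paired comparison estimates πμ1 + (1 − π)μ0.
- The hypothesis concerns μ1 − μ0, or the corresponding difference in baseline level.
- The first quantity does not determine the second. Baseline levels are never compared between patients at all.

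**Illustration.** Assumed values: 12 patients, 4 responders (π = 4/12), SD of change 1 within group, two-sided 0.05 t-tests, 10,000 simulated trials.

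| Case | μ1 | μ0 | Mean change | μ1 − μ0 | Paired test significant | Responder comparison significant |
|---|---|---|---|---|---|---|
| A: everyone shifts | 1 | 1 | 1 | 0 | 88% | 5% |
| B: change depends on response | 4/3 | −2/3 | (4/12)(4/3) − (8/12)(2/3) = 0 | 2 | under 1% | 83% |

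The paired test is usually positive where there is nothing to identify, and almost never positive where there is. The percentages depend on the assumed effects; the mismatch does not.

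**How precise the missing comparison would be.** One marker, all 12 patients sampled:

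- 4 versus 8: the 95% interval has half-width 2.228 × √(1/4 + 1/8) = 1.36 SD. A t-test has 80% power only at about 1.9 SD, and 32% power at 1 SD.
- 3 versus 9: 80% power needs about 2.1 SD.
- Smallest possible two-sided exact rank-sum p: 2/C(12,4) = 2/495 = 0.0040 with 4 responders; 2/220 = 0.0091 with 3; 2/12 = 0.17 with 1.
- Multiplicity: 0.05/12 = 0.0042, but 0.05/13 = 0.0038. With 4 responders, even perfect separation fails a Bonferroni correction beyond 12 markers. With 3 responders it fails beyond 5 (0.05/5 = 0.0100; 0.05/6 = 0.0083). The nine panels in 3.3 total 8+10+13+12+13+9+7+15+12 = 99 colours, counting repeated lineage markers.

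**Timing of samples.** Section 6.5 schedules blood before the first infusion, at 24, 48 and 72 hours, on days 7, 14 and 21, then before each dose through cycle 4. At 3-week intervals the fourth dose falls 9 weeks after the first. Section 6.3 places the response scan at week 12. On the planned schedule, the 6.5 samples therefore precede the response assessment. Section 7.1.1.13 also allows optional draws near imaging, and those may not.

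**The case against.** The strongest reply is that the objective is only to describe profiles before and after treatment, and 8.1.3 openly calls the work descriptive, exploratory and unpowered. A paired description meets that objective, and no success criterion rests on it. This stands as far as it goes, and it is why the point is minor. It excuses the lack of power; it does not excuse a hypothesis that the analysis cannot reach. Making the hypothesis purely descriptive would by itself remove the contradiction.

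A second reply also stands: the remedy would not prove who benefits either. In a single-arm trial, a marker associated with response may be prognostic rather than predictive. The added analysis can show association only.

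Three stronger readings are tempting and are not supported:

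- **That no other correlative analysis was planned.** Some text between the end of 8.1.2 and the start of 8.1.3 was not available for review. The statement holds for the readable text only.
- **That post-dose profiles can serve only as pharmacodynamics.** The samples through cycle 4 come before the week-12 scan, and the hypothesis covers profiles both before and after treatment without requiring selection before the first dose. Early change against response is a legitimate question, although early change may itself reflect a response already under way.
- **That 12 patients suffice to detect a strong association.** The smallest p of 0.0040 is for one marker, complete sampling and 4 responders. Blood is optional, biopsies are taken only when possible (2.1), and many markers are measured.

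**Conclusion.** The point holds for the text available. The within-subject comparison in 8.1.3 relates no profile to outcome, so it cannot address the hypothesis stated in 3.2 and 8.1.3, and a before/after shift says nothing about who benefits. This follows from the form of the analysis and rests on no assumed figure; the simulation only illustrates it. The conflict in rank between 3.2 and 8.1.3 is also real.

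The consequence is small. A reader might infer that the trial's main results are weakened. They are not: the primary safety and ORR analyses use no marker. The value of acting lies in fixing a modest analysis in advance and keeping the hypothesis within what 12 patients in a single arm can show.

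**What to change.** In 8.1.3:

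1. Keep the paired comparisons and label them as pharmacodynamic description.
2. Add a descriptive, exploratory comparison, between 3-month responders and non-responders, of (a) baseline profile and (b) early on-treatment change, using only samples taken before the week-12 scan. Report estimates with 95% confidence intervals and the number of patients sampled in each group.
3. Name a short list of key markers in advance, or state that results are not adjusted for multiplicity and only generate hypotheses.
4. Reword the hypothesis to say that profiles are associated with response. Note that a single-arm trial cannot separate predictive from prognostic markers, and that early change may reflect response.
5. Make no statement that a strong association would be detectable.

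In 3.2 and 8.1.3, give the objective one rank: exploratory.

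The cost is a few sentences and one small analysis on samples and scans already planned, with no new visits. The drawback is very low precision: about 4 versus 8 patients if ORR is 35% and everyone is sampled, and fewer if optional samples are missing. The plan should state this.
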